- a. Lengthen the time window of treatment for patients with fCIS from 6 hours to 24 hours. In doing so, we will offer useful treatment to patients who would otherwise be denied treatment under current standards.
- b. Encourage focusing on achieving good revascularization rather than limiting time during IAT for patients with fCIS.
- c. Improve the percentage of good outcomes in the treated population
- d. Save patients with pCIS from complications due to brain edema and intra-cranial hemorrhage that could potentially result from IAT
- e. Save the health care system the costs of futile treatment of patients with pCIS.

III. METHODS

A. Study Design:

Version: 6.0

The current study focuses on patients with acute ischemic stroke due to a blockage of the intracranial internal carotid artery or middle cerebral artery (M1). The study will be performed prospectively in up to 6 stroke centers. Akron General Medical Center is the primary institution for development of the study and data analysis for this multicenter trial. To participate in the study, all centers need to meet certain qualified requirements which include:

- One neurointerventionalist with 6 years' experience in performing IAT with multiple devices.
- Demonstrate coverage of the comprehensive stroke center 24 hours a day. The proposed study will be carried out over a period of 4 years from the initial approval date. Informed consent will be obtained for each patient, as described in section VIII. The study will be carried out in 2 phases (Figure 1).

Phase I will compare outcomes between treated patients with fCIS and pCIS. All eligible patients will be assessed by a full diagnostic cerebral angiogram with dye injection of all potential collaterals. DCA will be used to characterize the CIS. Treatment will be identical for both groups. All patients will be treated with the combination of IAT and the normal standard of care for a patient not receiving IAT (which may include IVT, but not always). The sample size will be set to have 60 patients complete the trial. Distribution of fCIS and pCIS patients will not be forced, but the option to balance groups may be employed if the percentage for one group reaches 70%.

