In phase II, after confirming the hypothesis that patients with pCIS tend to have poor outcomes as compared to the natural history of the disease, only patients with pCIS will be enrolled. 30 patients will be randomized into treatment including IAT or without IAT plus standard of care based on a simple 1:1 randomization. All otherwise IV tPA eligible patients will be treated with IVT using tPA regardless of the assigned group since this represents current standard of care. Based on previous studies, the results from Phase I should show poor results for pCIS patients, on the order of 15% good outcomes, below the published good outcomes for patients receiving no treatment. This phase will provide preliminary data to determine if IAT provides any benefit in these patients, or is even potentially harmful, which no other clinical trial to date of IAT has formally hypothesized or tested as plausible. Due to the low rate of success the investigators realize this phase will be underpowered to definitively show differences between two groups, but the phase will provide preliminary safety pilot data on a topic not studied to date to develop plans for a larger and adequately powered study.

All eligible patients participating in both phase I and phase II will be given the option to donate an additional 8.5 ml blood sample for genetic testing of the *Dce1* gene. Blood samples will be collected in Paxgene DNA tubes. Collection of this sample will occur during regularly scheduled blood work within 48-60 hours of admission. Akron General will store all samples until all patients are enrolled after which the samples will be sent to a biospecimen processing facility to identify polymorphisms of the *Dce1* gene. Results obtained from the genetic testing will be analyzed in conjunction with data from phase I and II.

The primary measure of outcome will be the same for both phases. The outcomes will be measured based on the modified Rankin Scale (see appendix) at least 3 months and again at 1 year following treatment. Patients will be graded according to this scale by an experienced

Version: 6.0

neurologist or other mRS scale certified health care provider not involved in the treatment and blinded to the treatment for each patient.

B. Study Population:

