For follow-up, patients will be seen by the participating neurologist at intervals typical of the standard of care. The primary outcome measure will be acquired at the 90 day follow up. At this appointment, a mRS score will be ascribed for the patient by a modified Rankin Scale certified health care provider blinded to the CIS categorization (phase I) or the treatment (phase II). Assessment based on the mRS is standard for follow up appointments, regardless of inclusion in the study. A standard follow up visit typically takes 15-30 minutes. For patients who cannot make it to the neurologist for a follow-up visit due to persistent significant handicap or limited access to transportation, mRS will be categorized over the phone by discussing the condition of the patient with a caregiver or nurse at the home or rehabilitation facility and the patient.

A secondary follow-up, patients will be seen by the participating neurologist at intervals typical of the standard of care. The primary outcome measure will be acquired at the 1 year follow up. At this appointment, a mRS score will be ascribed for the patient by a modified Rankin Scale certified health care provider blinded to the CIS categorization (phase I) or the treatment (phase II). Assessment based on the mRS is standard for follow up appointments, regardless of inclusion in the study. A standard follow up visit typically takes 15-30 minutes. For patients who cannot make it to the neurologist for a follow-up visit due to persistent significant handicap or limited access to transportation, mRS will be categorized over the phone by discussing the condition of the patient with a caregiver or nurse at the home or rehabilitation facility and the patient.

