Pre-operative condition and patients outcomes will be assessed using standardized and validated measures. The primary endpoint of a mRS score will be obtained at least 90 days following treatment and again at 1 year following treatment. NIHSS score will be obtained in the emergency room before the treatment, within 24 h of treatment, and before discharge. The person who will obtain the NIHSS will be certified to obtain it. Adequacy of revascularization will be assessed at the end of treatment by the treating physician according the modified thrombolysis in cerebral infarction (mTICI) scale (see Appendix). All of these measures are standards for care and trials of acute ischemic stroke. [8-10] All case report forms will be maintained by the primary investigator at the local site, and stored within locked cabinets. The personal identifying information on the case report forms will be deidentified and assigned a code before being transferred to Akron General Medical Center for transfer of the data to a de-identified database which will be used for analysis.

IV. DATA COLLECTION

Version: 6.0

A. How and what data will be collected

Data related to patient demographics, stroke risk factors, condition prior to treatment, time of treatment, and outcomes will be collected for each patient. Data on demographics will include sex, age, and race. Data on stroke risk factors will include history of hypertension, blood pressure, prior heart attack, arrhythmias, diabetes, glucose (sugar) level at admission, and obesity. Data on condition prior to treatment will include NIHSS score determined in the emergency room. Data on time of treatment will include time from symptoms to arrival at emergency room, time to start of DCA, and time to end of the procedure. Data on outcomes will include mRS at 3 months, mRS at 1 year, NIHSS score within 24 hours and at discharge, and complications brain edema and intra-cranial hemorrhage. Other parameters within these categories could be acquired as deemed necessary for analysis of the data.

V. DATA ANALYSIS

A. Sample Size Considerations

Phase I

A power analysis has been performed based on the previous retrospective analyses of the relationship between outcomes and the CIS for phase I. The sample size was calculated for the influence of the combination of CIS and revascularization on good outcomes (mRS \leq 2) based on the following assumptions.

- The percentage of patients with fCIS will be 60%

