- The percentage of patients with good revascularization will be 50%
- The rate of good outcomes for the combination of fCIS and good revascularization is assumed to be 70%
- The rate of good outcomes for the combination of fCIS and poor revascularization is assumed to be 20%
- The rate of good outcomes for the combination of pCIS and good revascularization is assumed to be 20%
- The rate of good outcomes for the combination of pCIS and poor revascularization is assumed to be 10%

The assumptions provide the following power analysis:

- $\alpha = 0.05$ for overall analysis and set to 0.025 for subgroup analysis comparing fCIS and good revascularization to all other groups due to multiple comparisons
- power = 0.90
- Needed Sample size = 54 patients
- An additional 6 patients completing the trial are budgeted due to risk of errors in estimated outcomes. An additional 15-20 patients are expected to be enrolled due to patients lost to the 90 day follow up and/or deviations from the protocol.

Phase II

Phase II will be an exploratory study evaluating the rates for good outcomes for patients with pCIS treated with IVT plus IAT vs. IVT (or other standard of care) only. The rate of good outcomes is expected to be approximately 13% for the IAT group with revascularization. The investigators have no prior data on expected rates of good outcomes for patients with pCIS treated with IVT only. The best possible outcome rate would be on

Version: 6.0

the order of 25% noted previously for untreated acute ischemic stroke. Due to the low levels of good outcomes, the investigators acknowledge the study will be underpowered to detect a difference between the two treatment groups for a total sample size of 30. Phase II will serve as a pilot study to initially establish estimates of rates of good outcomes for pCIS patients treated with IVT only for design of a larger prospective study.

Genetic Analysis

Genetic analysis will be performed based on the following:

- Genetic and expression analysis for the two groups based on their collateral score
- Adjust groups for cardiovascular/stroke risk factor presence and other known confounding conditions
- High density SNP array analysis will be performed for common and rare alleles
 against known collateral-related genes that have been identified in mice. These
 include human RABEP2 and its isoform RABEP1 and related gene pathways;
 VEGFA, FLK1 and their related gene pathways; NOTCH, DLL4, ADAM10,

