 ADAM17, CNX37 and their related gene pathways.
- Subgroup analysis will be performed for ethnicities.
- Taqman assays and/or exome sequencing of significantly associated SNPs and/or genes.
- Pending results, a future validation study will follow this discovery study by increasing the sample size.

B. Statistical Methodology

Data for the proposed study will be analyzed using comparison of proportions and multivariable logistic regression. Analysis of proportions based on Fisher exact tests will be used to compare rates of good outcomes between the fCIS and pCIS groups as the primary end point for phase I. The influence of successful revascularization on outcomes for patients with fCIS or pCIS will also be analyzed using Fisher exact tests as the secondary end point.

Binary and/or ordinal multiple logistic regression analyses will be used to evaluate the influence of multiple parameters on the likelihood of a good outcome. These parameters will include CIS, mTICI score, NIHSS score, time to revascularization, age, sex, history of diabetes mellitus, history of high blood pressure, history of coronary artery disease. The same analyses will be performed for phase II, instead focusing on the treatment groups rather than the CIS classification.

VI. DATA AND SAFETY MONITORING PLAN

A. Describe any provisions for monitoring the data for safety

A safety committee will monitor the data. The safety committee will be composed of at least 3 voting members. At least two members will be neurologists, neuroradiologists or neurointerventionalists with experience treating acute ischemic stroke who are not investigators at any of the sites. These members will not be affiliated with the institution of the principal investigator, any sub- investigator, or Akron General Medical Center. At least one member with a background in biostatistics who is not an investigator or affiliated with Akron General Medical Center will also be on the committee.

For phase I, the only deviations in normal standards of care are:

Version: 6.0

- 1- the extra few minutes for full DCA for some centers as opposed to injecting only the occluded vessel
- 2- Adding IAT to treatment of patients seen between 6 and 24 hours of onset of symptoms.

The safety committee will be looking at known potential complications for IAT in both fCIS and pCIS groups. These include:

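### The two descriptions of the Phase I mRS rater's blind differ and neither clearly withholds the revascularization result, which is the compared factor in the secondary endpoint and part of the 0.025 subgroup contrast

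*Combined protocol and SAP*

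**What the plan says.** Section III.D (Study Procedures) describes the mRS assessment twice, for 90 days and for 1 year, in the same terms. The score is given by a "modified Rankin Scale certified health care provider blinded to the CIS categorization (phase I) or the treatment (phase II"). It allows scoring by telephone, through a caregiver or nurse and the patient, when the patient cannot attend.

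Section III.A (Study Design), in a paragraph covering both phases, describes the rater differently: an experienced "neurologist or other mRS scale certified health care provider not involved in the treatment and blinded to the treatment for each patient". The same section says of the Phase I fCIS and pCIS groups: "Treatment will be identical for both groups".

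On revascularization, section III.D says: "Adequacy of revascularization will be assessed at the end of treatment by the treating physician", using the mTICI scale. No section says whether the mRS rater may see that grade.

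Revascularization enters the Phase I analysis in three ways:

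- **Secondary endpoint (V.B):** "The influence of successful revascularization on outcomes for patients with fCIS or pCIS will also be analyzed using Fisher exact tests".
- **Subgroup test (V.A):** alpha is set to 0.025 for the "subgroup analysis comparing fCIS and good revascularization to all other groups due to multiple comparisons".
- **Regression (V.B):** the mTICI score is a listed parameter.

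The primary analysis in V.B is to "compare rates of good outcomes between the fCIS and pCIS groups as the primary end point for phase I".

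**The concern.** An outcome rater should be blind to every factor whose effect on that outcome is to be tested. In Phase I there are two: CIS and revascularization. The visit procedure names only CIS. The design section names treatment, but every Phase I patient receives IAT and there is no allocation to conceal, so it is unclear whether the term reaches the result of the procedure.

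Good outcome is mRS 2 or lower. By the appendix, the line between 2 and 3 is whether the patient looks after their own affairs unaided or needs some help. That is a judgement, and by telephone it may rest on someone else's account. A rater who knows that the vessel was opened, or was not, may resolve a doubtful case in line with expectation. The analyses at stake are the secondary endpoint and the subgroup contrast. A score already influenced in this way cannot be corrected by later analysis.

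**Working it through.** **1. Is revascularization part of the basis for the sample size?** Section V.A says the size was calculated for the combination of CIS and revascularization. Its inputs are 60% fCIS, 50% good revascularization, and good-outcome rates of 70% (fCIS, good), 20% (fCIS, poor), 20% (pCIS, good) and 10% (pCIS, poor), with alpha 0.025 for the subgroup and power 0.90.

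Taking CIS and revascularization as independent (my assumption):

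- Share with fCIS and good revascularization: 0.6 × 0.5 = 0.30.
- Rate in all others: (0.3 × 0.20 + 0.2 × 0.20 + 0.2 × 0.10) / 0.7 = 0.1714.
- Allocation ratio k = 0.7/0.3; difference d = 0.70 − 0.1714 = 0.5286; pooled rate = 0.33.
- Two-sided 0.025: n = [2.241 × √(0.33 × 0.67 × (1 + 1/k)) + 1.282 × √(0.70 × 0.30 + 0.1714 × 0.8286/k)]² / d² = 13.3.
- Continuity correction: (13.3/4) × [1 + √(1 + 2(1 + 1/k)/(13.3 × 0.5286))]² = 15.9, so 16 patients in the subgroup.
- Total: 16/0.30 = 53.3, so 54.

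This matches the stated 54. The plan gives neither the test nor the sidedness, so the route is inferred; a four-group chi-square at 0.05 gives 53. Both routes use the revascularization split. Changing the blind leaves 54 as it is.

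**2. Cell sizes at 60 completers.**

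- fCIS: 60 × 0.6 × 0.5 = 18 per revascularization cell; one patient is 1/18 = 5.6 points.
- pCIS: 60 × 0.4 × 0.5 = 12 per cell; one patient is 1/12 = 8.3 points, against an assumed difference of 20% − 10% = 10 points.
- The assumed fCIS difference is 70% − 20% = 50 points.

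These figures show how sensitive the rates are. They do not estimate bias.

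**3. What a rater shift would do.** The documents give no rate of misrating, so the shift is my assumption, with a range of 0 to 20 points. A rater blind to CIS but aware of mTICI would raise opened vessels in both CIS strata. In the subgroup contrast the shift therefore applies to the 18 index patients and also to 12 of the 42 comparators. With no true effect of either factor, exact two-sided Fisher rejection rates are:

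| Shift (points) | Within fCIS, 18 v 18, nominal 5%: true rate 45% / 20% | Subgroup, 18 v 42, nominal 2.5%: true rate 45% / 20% |
|---|---|---|
| 0 | 2.8% / 2.0% | 1.9% / 1.6% |
| 5 | 3.6% / 2.9% | 2.4% / 2.3% |
| 10 | 5.9% / 5.3% | 3.5% / 3.8% |
| 15 | 10.0% / 9.5% | 5.4% / 6.2% |
| 20 | 16.1% / 15.9% | 8.5% / 9.8% |

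At 5 points neither test exceeds its nominal level. At 10 points both do, by a little.

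**4. The primary comparison.** If half of each CIS group is well revascularized, a shift of s raises both groups' rates by 0.5 × s and their difference does not move.

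**The case against.** The strongest reply is that section III.A already covers most of this. A reader might infer from section III.D that the rater is blinded to CIS alone. The documents do not support that: III.A, for both phases, also requires a rater outside the treatment and blinded to it for each patient. Treatment is identical between CIS groups, not patient by patient. Standard of care may or may not include IVT, and the Trevo device is only the first pass. So the phrase has some content in Phase I and can fairly be read to put the procedure note out of bounds. Also, the CIS is read from the angiogram done just before clot removal (section I.C), so opening those records could break the CIS blind as well.

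This narrows the point and does not close it. A treatment and its result are different things, the visit procedure gives a different Phase I blind, and no text mentions the mTICI grade. What stands is that access is limited but not clearly excluded. Nothing shows that raters will in fact know the result.

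A reader might also infer that any bias favours the investigators' hypothesis throughout. It does so in fCIS. In pCIS, section I.D expects revascularization to be futile, so raising the scores of opened vessels would work against the hypothesis.

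Finally, shifting only the 18 index patients in the subgroup contrast would give 5.3% at 10 points (true rate 45%). That overstates the effect: a CIS-blind rater would shift the 12 pCIS comparators with opened vessels too, which gives 3.5%.

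**Conclusion.** The point holds as a gap between two sections. They describe the Phase I rater's blind differently, and neither clearly withholds revascularization, although that factor is tested in the secondary endpoint and helps define the 0.025 subgroup. The likely direction is a larger apparent revascularization effect in both CIS strata.

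The size is unknown. Under an assumed 10-point shift, no true effect, and the planned 60 completers split 60/40 and 50/50, the inflation is modest: about one point above nominal in each test at a true rate of 45%. It becomes material only at shifts of 15 to 20 points, for which the documents give no evidence.

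A reader might infer that the Phase I primary result is compromised. It is not directly affected: the rater is expressly blinded to CIS, and under the plan's equal-revascularization assumption the shift cancels. Since the remedy is cheap and biased ratings cannot be repaired later, the change is worth making.

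**What to change.** Reconcile sections III.A and III.D so that both give one rule for Phase I: the mRS rater is not involved in the patient's treatment and is blinded to the CIS, the mTICI grade and the angiography and procedure records. Apply it at 90 days and at 1 year, and to telephone ratings. Add a site instruction that the rater scores from the mRS form without opening those records.

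The cost is one sentence and the instruction. A certified rater independent of treatment is already required, so no assessor is added, and the sample size and analyses stay as they are. The small downside is that the rater cannot consult the procedure notes.
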